2 GENERAL AND TECHNICAL ASPECTS

The objective of this statistical analysis plan (SAP) is to specify the statistical analyses with appropriate detail and precision to serve as a guideline for statistical programming and creation of tables, figures, and listings for clinical study protocol M930521001 (version 3.0), dated 29-Aug-2020 and the following amendment (version 4.0), dated 10-Jun-2020.

All programs will be written using SAS version 9.4. A preferred font size of 10 points, minimum font size of 8 points with a unique font size for the whole document required will be used for the tables and figures in section 14 for an output in A4 landscape format. For listings, a minimum font size of 9 points will be used to produce the output in A4 format. Individual SAS programs will be written for all tables, figures, and listings. All outputs will be transferred into PDF files using the Metronomia internal procedures. These PDF files will be generated as needed to populate the subsections of Section 14 and Section 16.2 for the clinical study report. Each PDF file will include the corresponding table of contents, preceding the content of the file. Special attention will be paid to planning and performance of quality control measures as documented in the QC plan for the analysis of this study.

The Merz standard Tables, Figures, and Listings (TFLs) for medical devices, version 2.0 (18-Feb-2020) will be applied and adapted to study specific requirements as laid down in the clinical study protocol and any amendments.

3 CLINICAL STUDY DESIGN AND OBJECTIVES

3.1 Clinical Study Design

This investigation is a 52 weeks prospective, multicenter, parallel-group, randomized clinical investigation with [REDACTED] to the treatment assignment [REDACTED] [REDACTED]. A [REDACTED] was chosen to minimize bias due to demand characteristics (i.e. what the evaluator expects). A parallel-group design was chosen to evaluate two different treatment regimens in one study. 9 sites were chosen to increase representativeness of the investigational results and to reduce site-associated biases. The treating investigators [REDACTED] that (will) participate in the investigation are board-certified dermatologists and/or plastic surgeons trained and qualified on the MAS. The [REDACTED] that (will) participate in the investigation are physicians or scientific experts, experienced in the area of aesthetic medicine, and also trained and qualified on the MAS.

Subjects have been randomized 1:1 either to treatment group A or treatment group B:

[REDACTED]

Number of visits:

Subjects have been assigned to attend overall 6 visits [REDACTED] [REDACTED]. The treatment visits were followed by 24 or at latest 48 hours post-injection telephone contacts. On injection visits, all investigation assessments were conducted before injection.

When COVID-19 public health emergency measures were implemented in Germany in spring 2020, it was foreseeable that not all subjects could come to all their post-baseline visits in due time. Therefore, time windows of early post-baseline visits have been widened and time points of later post-baseline visits have been adjusted. [REDACTED]

[figure not shown]
3.2 Clinical Study Objectives

Primary objectives

- To evaluate the effectiveness and safety of MRZF111 treatment for improvement of décolleté wrinkles as assessed on the MAS Décolleté Wrinkles – At Rest.

Secondary objectives

- To evaluate the effectiveness of MRZF111 treatment for improvement of décolleté wrinkles as assessed on the MAS Décolleté Wrinkles – Dynamic.
- To evaluate the subject's and physician's treatment satisfaction assessment after MRZF111 treatment of the décolleté.
- To evaluate the subjects and physician's global aesthetic improvement (GAIS-Wrinkles) after MRZF111 treatment of the décolleté.

4 DETERMINATION OF SAMPLE SIZE

The primary effectiveness endpoint is the proportion of subjects with at least 1 point (≥ 1 point) improvement on the MAS Décolleté Wrinkles – At Rest scale at 16 weeks after last treatment compared to baseline (Day 1). [REDACTED]. By use of a one-sided binomial test, it will be tested at an error level of 2.5% whether the response rate is significantly larger than 50%. It is aimed to ensure a power of 90%. The binomial test is applied to the pooled data from both treatment groups. [REDACTED]

Per definition, the safety evaluation set (SES) will be at least as large as the FAS. Thus, according to the above outlined assumptions, at least 100 subjects are planned to be available for safety analyses. This sample size is sufficient to observe, with a probability of 80%, at least one adverse event with actual event probability of 1.6%.

With regard to safety analyses, it should be considered that the RADIÉSSE® in its original undiluted form is marketed since 2003. Since then, over 5 million units had been sold and used in a variety of subject populations. In this period, the majority of reported AEs were common expected injection site reactions that were mild in nature and resolved over time. [REDACTED]

[REDACTED] The large extent of the exposure to the undiluted RADIÉSSE® worldwide versus the relatively small number of complications led to the conclusion that its safety has already been established to a sufficient degree. As it is not expected that dilution of RADIÉSSE® Volume Advantage 1.5 mL Injectable Implant with saline will cause more AEs, it is assumed the safety can be transferred to the IMD.

Consequently, the sample size for this study was primarily determined to ensure an adequate power for the primary effectiveness analysis, however, still providing a good probability of risk detection.

5 ANALYSIS SETS

The following analysis sets are defined for the statistical analysis of this clinical study:

Safety Evaluation Set (SES)

The SES is the subset of all randomized subjects who were exposed to the IMD at least once. Subjects will be analyzed as treated.

[figure not shown]

Full Analysis Set (FAS)

The FAS is the subset of subjects in the SES for whom at least the baseline value of the primary effectiveness variable is available (i.e., all subjects who have a baseline value on the MAS Décolleté Wrinkles – At Rest scale). In contrast to the SES, subjects will be analyzed as randomized.

Modified Full Analysis Set

The modified FAS is the subset of the subjects in the SES for whom at least the baseline value of the primary effectiveness variable is available (i.e., all subjects who have a baseline value on the MAS Décolleté Wrinkles – At Rest scale). Subjects will be analyzed as treated.

Per Protocol Set (PPS)

The PPS is the subset of subjects in the modified FAS without major protocol deviations. Subjects of treatment group A switching to treatment group B will not be excluded from the PPS per se, as this is in line with protocol amendment 4. Further major protocol deviations and other reasons leading to exclusion will be defined prior to database lock during a data review meeting (DRM).

6 ENDPOINTS FOR ANALYSIS

6.1 Effectiveness Endpoints

[figure not shown]
6.1.1 Primary Effectiveness Endpoint

[figure not shown]
The primary effectiveness endpoint is the proportion of subjects with at least 1-point (≥ 1 -point) improvement on the MAS 'Décolleté Wrinkles – At Rest' scale at 16 weeks after last treatment compared to baseline (Day 1). [REDACTED] A response is defined as ≥ 1 -point improvement on MAS 'Décolleté Wrinkles – At Rest' scale at 16 weeks after treatment compared to baseline (Day 1).

[figure not shown]
6.1.2 Secondary Effectiveness Endpoints

The secondary effectiveness endpoints are:

- Proportion of subjects with at least 1-point (≥ 1 -point) improvement on the MAS 'Décolleté Wrinkles – Dynamic' scale at 16 weeks after last treatment compared to baseline (Day 1). [REDACTED] A response is defined as ≥ 1 -point improvement on MAS 'Décolleté Wrinkles – Dynamic' scale at 16 weeks after treatment compared to baseline (Day 1).
- Treating investigator's treatment satisfaction assessment of aesthetic improvement in the subject after the décolleté treatments 16 weeks after last treatment.
- Subject's treatment satisfaction assessment of aesthetic improvement after the décolleté treatments 16 weeks after last treatment.
- Treating investigator's evaluation of the global aesthetic improvement on the Investigator's Global Aesthetic Improvement Scale (iGAIS) [REDACTED].
- Subject's evaluation of the global aesthetic improvement on the Subject's Global Aesthetic Improvement Scale (sGAIS) [REDACTED].

[figure not shown]
6.2 Safety Endpoints

[figure not shown]
6.2.1 Primary Safety Endpoints

Not applicable.

6.2.2 Secondary Safety Endpoints

- Incidence of TEAEs related to the treatment with the IMD.

7 STATISTICAL ANALYSIS METHODS

In the following, the term “treatment group” refers to the realized treatment group. This may differ from the randomized treatment group as those subjects randomized to group A [REDACTED] who did not manage to get their second injection in due time due to the COVID-19 public health emergency measures were allowed to skip this treatment and proceed with the last foreseen treatment. By this measure, these subjects switched to treatment group B [REDACTED]. Assuming that the mechanism of being prevented from performing the second treatment visit due to COVID-19 public health emergency measures is independent from any known or unknown, potentially confounding factors, the realized treatment groups should still be comparable in their baseline characteristics and analyses on them of high scientific value.

In the sections below, baseline severity refers to the severity of wrinkles on the MAS ‘Décolleté Wrinkles – At Rest’ as assessed [REDACTED].

For all analyses concerning ‘16 weeks after last treatment’, assessments of the visit closest to 16 weeks after last treatment within the time frame of 12 to 20 weeks after last treatment will be used. In case no visit was performed in the specific time frame, the assessments for ‘16 weeks after last treatment’ will be treated as missing.

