1 SYNOPSIS

Investigation title

Prospective, multicenter, parallel-group, evaluator-blind, randomized study to investigate the effectiveness and safety of MRZF111 in the treatment of décolleté wrinkles.

Indication

Improvement of décolleté wrinkles and skin quality.

Investigation objectives

Primary objectives

• To evaluate the effectiveness and safety of MRZF111 treatment for improvement of décolleté wrinkles as assessed on the Merz Aesthetic Scale (MAS) Décolleté Wrinkles-At Rest.

Secondary objectives

- To evaluate the effectiveness of MRZF111 treatment for improvement of décolleté wrinkles as assessed on the MAS Décolleté Wrinkles-Dynamic.
- To evaluate the subjects and physician's treatment satisfaction assessment after MRZF111 treatment of the décolleté.
- To evaluate the subjects and physician's global aesthetic improvement on Décolleté Wrinkles (GAIS-Wrinkles) after MRZF111 treatment of the décolleté.

Subject population, diagnosis, and main criteria for in- and exclusion

A total of approximately 112 adult females will be enrolled if they meet all of the inclusion and none of the exclusion criteria. The enrolment period will be 12 weeks in total.

Main inclusion criteria

- Female between ≥ 18 and ≤ 65 years old.
- Décolleté wrinkles with a rating of moderate to severe (grade 2 to 3) on the MAS Décolleté Wrinkles-At Rest as determined and confirmed by the treating investigator afterwards.

Main exclusion criteria

- Any previous treatment with fat injections, poly L-lactic acid or permanent dermal fillers (e.g., silicone, polymethyl methacrylate) in the décolleté.
- Any previous surgery, including plastic surgery, or surgical permanent implant in the décolleté or in the breasts that could interfere with effectiveness and safety.

- Any previous thread lifting in the décolleté.
- Previous treatment with collagen fillers, calcium hydroxylapatite (CaHa), and/or long-lasting hyaluronic acid (HA) fillers (e.g., Belotero Intense/Volume, Juvéderm Volift/Volbella) in the décolleté within the past 24 months before baseline.
- Previous treatment with other HA fillers in the décolleté within the past 12 months before baseline.
- Previous treatment with botulinum toxin, ablative or fractional laser, microdermabrasion, microneedling, chemical peels and/or non-invasive skin-tightening (e.g., ultrasound, radiofrequency, intense pulsed light treatment) in the décolleté within the past 6 months before baseline.

Investigational medical device

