The final applied IMD MRZF111 is RADIESSE® Volume Advantage 1.5 mL Injectable Implant . The injection of MRZF111 peeds to be done directly often dilution.

MRZF111 needs to be done directly after dilution.

MRZF111 is prepared using a MRZF111

Investigation design

This investigation is 52-weeks prospective, multicenter, parallel-group, randomized clinical investigation with live assessments

. The treating investigators that will participate in the investigation are board-certified dermatologists and/or plastic surgeons trained and qualified on the MAS.

Approximately 112 female subjects with moderate or severe wrinkles (grade 2 or 3) on the MAS Décolleté Wrinkles-At Rest seeking improvement in décolleté wrinkles who agree to participate by signing the informed consent form and who satisfy all inclusion and exclusion criteria will be enrolled.

aseline severity scores will be assessed live according to the MAS by the treating investigator and the subject. Biophysical skin quality parameters (Cutometer[®], Ultrascan[®]) and skin microstructure appearance will be obtained instrumentally from each subject's treatment area by selected trained sites.

either to treatment group A or treatment group B to the following treatment regimen:

- Treatment group A is assigned
- Treatment group B is assigned

A parallel-group design was chosen to evaluate two different treatment algorithms at once.

The primary objective of effectiveness for both treatment groups will be assessed at 16 weeks after last treatment (approximately Week 32). Response is defined as \geq 1-point improvement on the MAS Décolleté Wrinkles-At Rest from baseline to 16 weeks after last treatment as assessed by who is **not aware** of the treatment regimen.

rating by the treating investigator, the subject self-assessment on the MAS (At Rest and Dynamic), and biophysical skin quality parameter measurements (at selected sites only) will be performed at baseline visit and at each follow up visit.

Subject's and Investigator's Treatment Satisfaction Questionnaire, Global Aesthetic Improvement Scales on Décolleté Wrinkles (GAIS-Wrinkles) and Global Aesthetic Improvement Scale on Décolleté Skin Quality (GAIS-Skin Quality) will be completed at all follow-up visits.

Medical safety

assessment will be done at each follow up visit. Planned investigational period

First subject first visit: Dec-2019

Last primary outcome visit: Oct-2020

Last subject last visit: Feb-2021

Duration of treatment per subject

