The duration of treatment is approximately 4 months per subject.

Endpoints for analysis

Primary Effectiveness Endpoint

Proportion of subjects with ≥ 1 -point improvement on the MAS Décolleté Wrinkles-At Rest scale at 16 weeks after last treatment compared to baseline (Day 1).

Secondary Effectiveness Endpoints

- Proportion of subjects with ≥ 1-point improvement on the MAS Décolleté Wrinkles – Dynamic scale at 16 weeks after last treatment compared to baseline (Day 1).
- Treating investigators treatment satisfaction assessment of aesthetic improvement in the subject after the décolleté treatments 16 weeks after last treatment.
- Subjects treatment satisfaction assessment of aesthetic improvement after the décolleté treatments 16 weeks after last treatment.
- Treating investigator's evaluation of the global aesthetic improvement on the investigator GAIS-Wrinkles (iGAIS-Wrinkles) from baseline (Day 1) to 16 weeks after last treatment.
- Subject's evaluation of the global aesthetic improvement on the subject GAIS-Wrinkles (sGAIS-Wrinkles) from baseline (Day 1) to 16 weeks after last treatment.

Secondary Safety Endpoints

• Incidence of TEAEs related to the treatment with the IMD.

Total number of subjects and number of countries

A total of approximately 112 adult females will be enrolled in Germany.

Number of investigation sites

Up to 10 sites.

Number of visits

Subjects are assigned to attend overall 6 visits

24 or at latest 48 hours post-injection telephone contacts.

Investigational product(s), volume and mode of injection

The final applied IMD MRZF111 is RADIESSE® Volume Advantage 1.5 mL Injecta	ble
Implant . The injection	of
MRZF111 needs to be done directly after dilution.	
MRZF111 is prepared using a MRZF111 kit	
Both groups (treatment group A a	and
treatment group B) will be treated with IMD at each injection visit	

Statistical analysis methods

The primary and secondary effectiveness endpoints will be summarized using the modified Full Analysis Set (FAS

. For sensitivity purposes, these analyses will also be performed on the modified FAS with observed data and on the Per Protocol Set (PPS). All remaining effectiveness endpoints will be summarized on the modified FAS population on observed data. Additional information related to the usage of the analysis sets as it relates to the statistical analyses of investigational results will be described in the Statistical Analysis Plan (SAP).

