6.2 Discussion of Investigational Design, Including Choice of Control Groups

The prospective, parallel-group, randomized, multicenter investigational design was chosen to adequately investigate the effectiveness and safety of the IMD.

In general, prospective designs can achieve a higher data quality compared to retrospective designs because they usually have fewer potential sources of bias and confounding than retrospective studies. A disadvantage of prospective studies is the risk of bias such as the loss of individuals to follow up during the investigation.

Up to 10 sites were chosen to improve data homogenization and to minimize siteassociated biases. Using several investigation sites increases the representativeness of the investigational results and decreases investigation site-related biases.

All the do not know which treatment protocol was applied (either 2 or 3 injection cycles) which helps minimize bias due to demand characteristics (what the evaluator expects). As this investigation has no control group, the subject and the treating investigator cannot be blinded.

A parallel-group design was chosen to evaluate two different treatment algorithms at once. Randomization eliminates bias in treatment assignment, specifically selection bias and confounding.

The general duration of 52 weeks will also allow assessing the late-onset reactions [Bass 2010, Smith 2007].

The injection technique approach follows the consensus guidelines mentioned above: the IMD has to be placed in th

Rationale

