7.1.1 Primary Effectiveness Endpoint(s)

The primary effectiveness endpoint is the proportion of responders (responder rate) defined as subjects with ≥ 1 -point improvement on the MAS 'Décolleté Wrinkles – At Rest' from baseline to 16 weeks after last treatment as assessed [REDACTED].

The primary analysis will be based on a one-sided binomial test at the one-sided type I error level of $\alpha = 0.025$ for the pooled data from both treatments against the null-hypothesis that the response rate (R) is $\leq 50\%$:

$$H_0 : R \leq 50\%$$

$$H_1 : R > 50\%.$$

H_0 is rejected if the resulting one-sided p-value is <0.025 and the observed proportion of responders is >0.5 .

As further supportive explorative analyses, the effectiveness for the different time points of treatments with a 16 weeks post-treatment period in both treatment groups will be analyzed as for the primary endpoint:

- Proportion of responders (response rate) defined as subjects with ≥ 1 -point improvement on the 'MAS Décolleté Wrinkles – At Rest' from last treatment application to 16 weeks after last treatment as assessed [REDACTED].
- Proportion of responders (response rate) defined as subjects with ≥ 1 -point improvement on the MAS 'Décolleté Wrinkles – At Rest' from last treatment application to 16 weeks after last treatment as assessed [REDACTED].
- Proportion of responders (response rate) defined as subjects with ≥ 1 -point improvement on the MAS 'Décolleté Wrinkles – At Rest' from baseline to 16 weeks after first treatment as assessed [REDACTED].

In addition, two-sided 95% Wilson score confidence intervals for response rates will be provided overall, and for each treatment group in the supportive analyses. A similar SAS code as given above will be used.

The primary effectiveness analyses will be based on the modified FAS with missing data replaced by a multiple imputation approach for each realized treatment group.

Sensitivity analyses of the primary endpoint will be provided based on observed cases only in the modified FAS and on the observed cases in the PPS. The supportive explorative analyses will be performed on the observed cases in the modified FAS as well as on observed cases in the FAS. For analysis based on observed data, SAS code similar to the following will be used:

```
proc freq data = dataset order = freq;  
  tables response / binomial (level="1" wilson p=.5) cl alpha=.05;  
run;
```

, assuming the response is coded with '1' and no response is coded with '0'.

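### By-regimen results on realized groups are open to confounding by calendar period, because a COVID skip of injection 2 depends on enrolment date

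*SAP*

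**What the plan says.** SAP section 7 defines treatment group as the realized group. Subjects randomized to A who could not attend for injection 2 in time because of COVID measures "were allowed to skip this treatment and proceed with the last foreseen treatment", and from then on they belong to group B. Protocol section 6.2 gives the regimens as "either 2 or 3 injection cycles"; the switch rule implies that A has three and B two.

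The SAP supports this grouping with an assumption, worded as such: that "being prevented from performing the second treatment visit due to COVID-19 public health emergency measures is independent from any known or unknown" potentially confounding factor. From it the SAP concludes that the realized groups should remain comparable at baseline and that analyses of them have high scientific value.

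The calendar is in the Protocol synopsis ("First subject first visit: Dec-2019"; "The enrolment period will be 12 weeks in total"; "The duration of treatment is approximately 4 months per subject") and in SAP section 3.1 ("When COVID-19 public health emergency measures were implemented in Germany in spring 2020").

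Under SAP section 7.1, effectiveness statistics are given pooled and by realized group. Under section 7.1.1 the primary analysis has "missing data replaced by a multiple imputation approach for each realized treatment group". SAP sections 7.1, 7.1.1 and 7.4.5 repeat the supportive exploratory analyses as randomized, on observed cases in the FAS, and section 7.1.2 extends the same set to the Dynamic scale.

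**The concern.** A group A subject whose injection 2 fell before the measures began could not miss it because of them. One whose injection 2 fell later could. Day 1 date is therefore a known determinant of the switch. Switching goes in one direction only, so it takes later enrollees out of A and adds them to B. Randomization balanced enrolment date in expectation; relabelling by realized regimen undoes that.

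Enrolment date also fixes the season of the baseline and Week 32 ratings and how far later visits were rescheduled. If either affects the ratings, a difference between realized A and realized B could reflect period rather than number of injections. This matters because Protocol section 4.2 names finding the appropriate regimen as an aim, and section 6.1 says the parallel groups are there to compare regimens.

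**Working it through.** **1. The planned calendar.** Take 12 weeks of enrolment, the primary visit at about Week 32 and the last visit at Week 52.
- First visit 1 December 2019: last enrolment 23 February 2020, last Week 32 visit 4 October 2020, last Week 52 visit 21 February 2021.
- First visit 8 December 2019: 1 March 2020, 11 October 2020 and 28 February 2021.

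Both reproduce the synopsis (last primary outcome visit October 2020, last subject last visit February 2021). A first visit on 15 December puts the last Week 52 visit at 7 March 2021, so the plan points to early December. These are planned dates, not actual ones.

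**2. When injection 2 was due.** The week is redacted. The last injection is at about Week 32 − 16 = Week 16, so I assume the midpoint, Week 8. With a first visit on 1 December, injection 2 then falls between 26 January and 19 April 2020. The start of the measures is given only as spring 2020; I assume 15 March.

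**3. Share due after the measures began** (uniform enrolment assumed). The cut-off enrolment date is 15 March minus 8 weeks = 19 January, which is 7 weeks after 1 December. Late share h = (12 − 7)/12 = 42%. For Week 6 it is 3/12 = 25%; for Week 10, 7/12 = 58%. At Week 8, with the measures between 1 and 20 March and the first visit between 1 and 8 December, h is 36% to 67%. Over Week 4 to Week 12 it is 2% to 100%.

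**4. Mix of the realized groups.** There are 56 per arm (Protocol section 12.1), so late A = late B = 56 × 5/12 = 23.3. If a share q of late A skips, s = 23.3q subjects switch.
- Late share of realized A = (23.3 − s)/(56 − s)
- Late share of realized B = (23.3 + s)/(56 + s)

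Under uniform enrolment, late enrollees join on average 6 weeks after early ones, so the enrolment gap is 6 weeks × the difference in late shares. The spurious A-minus-B difference is the difference in late shares × the period effect (early versus late response rate).

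| q | switchers | late in A | late in B | difference | enrolment gap | shift, 10-point period effect | shift, 20-point |
|---|---|---|---|---|---|---|---|
| 25% | 5.8 | 35% | 47% | 12 points | 0.7 weeks | 1.2 | 2.5 |
| 50% | 11.7 | 26% | 52% | 25 points | 1.5 weeks | 2.5 | 5.1 |
| 75% | 17.5 | 15% | 56% | 40 points | 2.4 weeks | 4.0 | 8.1 |
| 100% | 23.3 | 0% | 59% | 59 points | 3.5 weeks | 5.9 | 11.8 |

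Across h = 36% to 67% and q = 25% to 100%, the gap is about 0.7 to 4.8 weeks, and the shift is about 1.1 to 8.0 points per 10 points of period effect. With no period effect it is zero. The period effects are illustrations; the documents give none.

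**5. What the as-randomized analyses cover.** Protocol section 12.4.1.1 lists three supportive analyses: change from last injection to 16 weeks after it in A, the same in B, and change from baseline to 16 weeks after the first injection in B. None is the primary response (baseline to 16 weeks after last injection) by randomized group. In the visible text, that response by regimen appears only for realized groups.

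**The case against.** - **The SAP makes a conditional statement about confounders.** It does not claim that the skip is unrelated to everything, and enrolment date contradicts it only if enrolment date also affects outcome. That is right. Protocol section 4.1 describes chronic sun exposure and ageing, not seasonal change in a wrinkle grade. A reader might infer that the by-regimen results are confounded; the documents give a possible route (sun exposure, rescheduled visits) but no size, so they support only that the results are open to it.
- **As-randomized FAS analyses are already planned.** They have no expected imbalance in enrolment date and do reduce the problem, but step 5 shows that, as listed, they miss the primary response.
- **The stakes are low.** No test of A against B is visible, and Protocol section 12.4.4.4 calls the separate-group tests explorative. With about 44 and 68 subjects, a 95% interval for A minus B is roughly ±18 to 19 points at assumed response rates of 67% and 50%, so a shift of a few points would be well inside it. This bears on priority; it does not make the assumption sounder.
- **Key inputs are unseen.** The injection 2 week, the number of switchers and the imputation model are not visible. If injection 2 was due near Week 4 or Week 12, almost none or almost all of group A was due after the measures began, and the tie to the calendar weakens. Nobody can say from these documents that period is absent from the imputation model.
- **A stratum due before the measures is not fully clean.** Visit windows were widened, so a subject due shortly before the measures could still have missed the visit. This stands and limits what stratification can claim.

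**Conclusion.** The independence assumption is not credible as written for enrolment date. On the planned calendar, with injection 2 around the midpoint of treatment, the switch depends on Day 1 date and runs only from A to B. Realized A is then likely weighted to earlier enrollees and realized B to later ones, and comparisons by realized regimen are open to, but not shown to be affected by, confounding by calendar period. In the central case the late shares are 26% and 52%. The resulting bias depends on the redacted injection 2 week, the number of switchers and an unknown period effect, and may be zero.

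A reader might also infer that the primary result is at risk. The pooled one-sample test does not depend on who is labelled A or B, except indirectly through imputation within realized group.

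The SAP describes randomization as complete and cites a source accessed in August 2020, so Day 1 dates existed and the assumption could have been checked. No visible text does so. This is a cheap improvement to exploratory analyses, not a threat to the confirmatory conclusion.

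**What to change.** 1. Qualify the independence statement in SAP section 7: say that the skip is expected to depend on enrolment date and that comparability of the realized groups is to be examined. Keep the assumption visible rather than deleting it.
2. Tabulate switchers, and realized A and B, by Day 1 date.
3. Report the primary and the Dynamic MAS response by randomized group (FAS) beside each realized-group result. State that the former describes assignment, including skips, and the latter the regimen received.
4. Add one sensitivity analysis of these by-regimen response rates, stratified by whether injection 2 was due before or after the measures began. Derive this for both arms from Day 1 plus the scheduled interval, with the start date of the measures fixed in the SAP. Show randomized-group results within strata, because realized groups in the later stratum remain non-randomized. Describe the earlier stratum as least exposed to COVID switching, not as clean. Other tables need not be stratified.
5. Include this indicator in the imputation model if it is not already there.

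The cost is SAP wording, one variable derived from dates already collected, a few extra tables, and wide intervals in small exploratory strata.
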